#### **D. Description, Risks and Justification of Procedures and Data Collection Tools:**

##### Risks:

Wearing insulin infusion sets and sensors can cause adverse skin reactions such as pain at the site of infusion set or sensor insertion. The adhesive pads may cause skin erythema for 1 to 2 days or more. An allergic reaction to 1 or more parts of CSII and CGM devices may occur which can be mild, moderate, or severe (rare). In rare cases, an infection at the infusion set or sensor site may occur. In rare cases, the sensor or needle may break inside the body and would require a minor surgical procedure to remove it.

These risks are likely during the run-in phase, but individuals unable to wear devices will not continue on. We also screen out individuals with a history of serious skin reactions to adhesives. These issues remain possible as the study continues, but will be less likely in those women able to be randomized.

Severe hypoglycemia is defined as a hypoglycemic episode requiring assistance of a 3rd party or hospitalization with or without an SMBG. The risk of severe hypoglycemia is high in pregnancy, especially in the 1st trimester. It will be reported as a severe adverse event (SAE). A hypoglycemic event “requiring assistance” is determined when the subject is unable to treat the event on her own. We have determined our sample size based on the ability to compare rates of severe hypoglycemia between groups. Severe hypoglycemia can lead to coma, seizure, or death, however the likelihood of these extreme adverse events is low. Any untoward event resulting in hospitalization, extension of hospitalization, death, or threat of death will also be considered an SAE. SAEs will be reported to the Drug Safety Monitoring Board (DSMB).

Medtronic CGM systems may experience reduced sensor accuracy (falsely elevated glucose levels) if the user takes acetaminophen-containing products. The level of sensor glucose inaccuracy may vary by participant and may depend on the quantity of acetaminophen administered. Therefore, all participants will be advised to mark acetaminophen use on paper and in the insulin pump as an “Injection” event marker. They will also be advised to rely on fingerstick glucose measurements for 12 hours after acetaminophen use for insulin dosing.

Pregnancies complicated by diabetes are inherently high-risk for adverse outcomes such as fetal loss, gestational hypertensive disorders, congenital malformations, abnormal fetal size, cesarean delivery, neonatal jaundice, neonatal hypoglycemia, and the like. SAPT has been used in pregnancy in previous studies and does not appear to significantly increase these risks in most cases. We do not anticipate that the HCL therapy used in this study will significantly increase these risks either. A viable pregnancy is defined as a pregnancy with detectable blood or urine human chorionic gonadotropin (hCG) level and confirmation of a fetal heart beat by Doppler ultrasound. Fetal loss is defined as loss of a viable pregnancy.

There is a risk of a breach in confidentiality. Thus, a confidential subject database will be established to maintain study data. Data will be entered into REDCap (Research Electronic Data Capture). REDCap is an internal secure, computerized database system at the University of Colorado Denver. This system allows data entry, survey/questionnaire building, data exportation to statistical packages, and is HIPAA compliant. Each subject will be assigned an identification number, which will be used to code and identify all of that subject’s records. This will avoid the continual use of subject names. REDCap surveys can be sent to study participants via e-mail for direct input into the database. All study data will be locked in the PIs’ offices and all relevant computer study files will be input on staff computers, which are password protected and contain encryption software. Data storage will be take place on a secured server maintained by the University of Colorado. The server is backed up nightly and a copy of the back-up file is kept off site in a secure facility. Data access will be limited to study personnel. Study results may be presented in the form of posters, abstracts, oral presentations, or publications at academic meetings or in journals. In all forms of study result reporting, subject identification will not be disclosed. A study subject may access his/her protected health information at any time by requesting said information in writing of the investigator. The investigative team has been trained in IRB and HIPAA compliance issues and will maintain confidentiality and protect health information. The above-stated procedures have been highly effective in preventing

breaches of patient confidentiality for the prior and current research studies in which the PI has been and continues to be involved.

All AEs, reported spontaneously by the subject, as well as those noted by the investigator or study staff, regardless of seriousness, severity or expectedness will be recorded on source documents from the time of obtaining the informed consent.

Protection Against Risks:

*Consenting Procedures:*

Subjects will be recruited from the BDC and OSU diabetes clinics, which both contain experts in gestational diabetes care (site PIs). Some subjects may be referred to each center by maternal fetal medicine specialists who are aware of the study, but only the site PIs will be allowed to determine possible eligibility for study participation. Subjects will have to be patients at each center to be included in the study. Subjects meetings initial inclusion/exclusion criteria will be invited to sign informed consent. They will be taken to a private room where the consent form will be discussed with them in detail, they will be asked to state their understanding of the study procedures, and will be asked if they have any inquiries. All questions will be answered. If they do not feel comfortable to sign the consent form at that point, they will be allowed to take it home and re-read it, then contact us with any further questions and with their decision about enrollment. All subjects will be provided a copy of the signed consent form.

Site PIs will determine initial eligibility for study inclusion. They will go over the inclusion and exclusion criteria with each potential subject and discuss the study procedures with women interested in participating. Private consenting procedures will be performed by trained research staff (PIs or professional research assistants). Completed, signed consent forms will be kept in their original form by study staff and a copy will be provided to subjects. The date of consent procedure completion will be recorded in REDCap.

*Safety Monitoring:*

This study's risks are minimized by use of extensive inclusion and exclusion criteria and close monitoring of research subjects. The key personnel are qualified and experienced in all of the study procedures. The collaborators and consultants provide necessary expertise for ensuring the safety of subjects and the integrity of the study procedures. We will also use a volunteer Safety Officer to oversee the study's safety. The Safety Officer will be an independent investigator (not a member of the research team) with experience in similar clinical research. S/he will review reports of adverse events, recruitment and enrollment statistics (ethnicity and numbers of subjects disqualified, withdrawn, randomized, and who completed the study) every 6 months. This information will be reviewed during meetings with study investigators and recorded by the Safety Officer in meeting minutes. A Data and Safety Monitoring Board (DSMB) will also be established and led by the Safety Officer. The DSMB will be comprised of the Safety Officer (from the University of Colorado), and additional faculty members from outside the BDC or OSU who are selected by the JAEB Center for Health Research. It will be notified immediately of severe adverse events (SAEs). It will review the details of the SAE and the study protocol to determine if the SAE was possibly, definitely, or not related to study procedures. It will advise the study PI of its determination and of corrective action that needs to take place (if at all). The DSMB will be notified of SAEs within 1 business day. They will review the details of the SAE and the study protocol to determine if the SAE was possibly, definitely, or not related to study procedures. It will advise the study PI of its determination and of corrective action that needs to take place (if at all). The study PI will

manage and report the SAEs and AEs to the IRB. Study staff will also identify, evaluate, and report anticipated and unanticipated device-related AEs. Additionally, the DSMB will conduct phone or video conference calls every quarter to review all the SAEs and AEs that have taken place. The DSMB will also review the planned interim analyses of data (especially glucose <63 m/dL) after the first trimester in the first 5 participants of each group.

There are study MDs at each study site who will closely oversee and monitor the study. The study PI will continually review all adverse events during screening, data collection, and insulin delivery with SAPT or HCL therapy. Subjects who fail screening will be informed of the reasons for failure. Adverse events will be reported to the Safety Officer as they occur for each individual occurrence and monthly in aggregate form, as well as documented by standard IRB procedures and reported to them during the annual protocol review. All serious adverse events will be immediately reported to the Safety Officer, COMIRB, and OSU's IRB (if applicable) using the COMIRB Serious Adverse Report Event (SAE) form. The PI will sign each SAE and include a copy of the signed consent form of the subject with relevant sections highlighted. Serious adverse events are defined as death, life threatening injuries, inpatient hospitalization (other than that related to planned labor and delivery), persistent or significant disability/incapacity, and congenital anomaly/birth defect. All serious adverse events determined by COMIRB to be definitely, probably, or possibly related to the study or intervention will be addressed by COMIRB as appropriate with actions including but not limited to: protocol modification, consent form modification, modification of the timetable for continuing review requirements, new study enrollment suspension, or study suspension or termination. If the study is suspended or terminated, prompt reporting to the JDRF (the Juvenile Diabetes Research Foundation, who is sponsoring this study) will be provided. Events not requiring suspension or termination shall be reported during the annual progress report.

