#### **IV. Research Methods**

##### **A. Outcome Measure(s):**

###### **Primary Outcomes:**

- 1) Safety of HCL therapy compared to SAPT in women with T1D throughout gestation and the early post-partum period assessed through episodes of severe hypoglycemia and time spent with glucose <54 mg/dL.
- 2) Indices of glucose control and fear of hypoglycemia in pregnant women with T1D using HCL or SAPT therapy throughout pregnancy and early post-partum. Indices of glucose control are time spent in the glucose target ranges <54 mg/dL and <63 mg/dL (hypoglycemia), 63-140 mg/dL (time in range), and >140 mg/dL and >180 mg/dL (hyperglycemia). Fear of hypoglycemia is assessed as behavior, worry, and total scores of fear of hypoglycemia determined by the Hypoglycemia Fear Survey.

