(3) Safety Factors (SA 1): Subjects will be asked at each visit if they had any episodes of SH requiring the assistance of a 3rd party, DKA, adverse skin reactions, or hospitalizations since the last study visit. DKA in pregnancy will be defined as positive symptoms (nausea, vomiting, malaise, polyuria, polydipsia, abdominal pain, change in mental status) with positive laboratory findings (glucose >300 mg/dL, arterial pH <7.3, anion gap >12 mEq/L, elevated blood or urine ketone levels, serum bicarbonate <15 mEq/L) or medical documentation of DKA by a healthcare facility. Subjects will be instructed to contact study staff immediately should any of these events occur in between study visits. We will request records of any urgent care visits, emergency room visits, and hospital admissions that occurred. Time spent <54 mg/dL (SH range) will be collected through CGM data.

(4) Glycemic Factors (SA 2): Insulin pumps, glucose meters, and CGMs will be downloaded at each visit. Data collected will be used to calculate percent of time spent in glucose ranges (hypoglycemic: <54 and <63; in range: 63-140 (per recommendations from the International Consensus on Time in Range); hyperglycemic: >140, and >180 mg/dL), mean glucose  $\pm$  standard deviation, J index, High Blood Glucose Index (HBGI), Low Blood Glucose Index (LBGI), duration of hypoglycemic episodes, Mean Amplitude of Glycemic Excursions (MAGE), and Continuous Overall Net Glycemic Action (CONGAn). Subjects will download from study devices weekly from home using CareLink® Clinical Software. At study visits and weekly in between study visits, subjects will provide data on frequency and duration of open-mode and closed-loop HCL mode. Data will be confirmed through HCL pump downloads, along with the reasons HCL mode was exited.

(5) Psychological Factors (SA 2 and 3):

- (a) Fear of hypoglycemia: We will measure fear with the Hypoglycemia Fear Survey which is a psychometric instrument wherein subjects rank frequency of 10 behaviors and 17 worries based on a 5-point Likert scale.
- (b) Quality of life (QOL): We will measure QOL over the past 4 weeks with the MOS Short-Form 36 (SF-36) which uses a multi-item scale from 36 questions to assess 8 health concepts (physical functioning, physical role, emotional role, pain, general health, vitality, social functioning, and emotional well-being).

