#### F. Data Analysis Plan:

##### Statistical Analysis Plan:

Data will be blinded to the study statistician. For the **interim safety analysis**, after the first 5 participants in each group have completed the 1st trimester, we will analyze the interim data to compare episodes of SH between groups to ensure no increased risk of SH with HCL therapy. Episodes of SH will be used for the interim analysis as SH events can be life-threatening for pregnant women and their fetuses. If interim safety analyses demonstrate no increased harm in either group, then the statistician will remain blinded until the end of the study. If the interim safety analyses demonstrate increased harm in one group necessitating evaluation of whether the study should be stopped, then the statistician will be unblinded at that point.

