To address **Specific Aim 1**, we will compare percent of time spent in the SH range of <54 mg/dL on CGM (primary outcome) using a non-inferiority t-test with a margin of 1%. Counts of DKA and adverse skin reactions (secondary outcomes) will be compared between groups (HCL vs. SAPT) using t-tests for normally distributed variables and Wilcoxon Rank-Sum test for non-normal variables. As the purpose of this study is to demonstrate that HCL has a similar safety profile compared to SAPT during pregnancy, we will use a non-inferiority test. As a secondary analysis of events such as SH, DKA, and skin reactions, we will account for potential differential follow-up times due to miscarriage, drop-out, and withdrawal using Poisson regression with an offset for follow-up time. To address **Specific Aim 2**, we will compare CGM glucose variables (primary outcomes for glucose variables will be time spent <54, <63, 63-140, >140, >180 mg/dL; secondary outcomes will be glucose SD, J index, HBGI, LBG, MAGE, and CONGAn) and fear of hypoglycemia score between groups (HCL vs. SAPT) using t-tests for normally distributed variables and Wilcoxon Rank-Sum test for non-normally distributed variables. We will examine the buckets of time spent in each range (hypoglycemia, in range, and hyperglycemia) by day and night, as well as day-to-day variation. Mean glucose variables and hypoglycemia fear scores will be compared during each trimester of pregnancy and 4-6 weeks post-partum using mixed models. To address **Specific Aim 3**, we will compare SF-36 scores, insulin device satisfaction and glucose device satisfaction by group (HCL vs. SAPT) using t-tests if scores are normally distributed and Wilcoxon Rank-Sum test if scores are non-normal. We will analyze changes in INSPIRE Questionnaire scores over time in the HCL group. **Specific Aim 4** is an exploratory aim, and for this aim we will examine rates of fetal loss, preeclampsia, cesarean section, LGA, and neonatal hypoglycemia using Chi-square tests. We will account for potential differential follow-up times due to miscarriage, drop-out, and withdrawal using Poisson regression with an offset for follow-up time as a sensitivity analysis, in addition to the proposed chi-square tests in the exploratory analyses of fetal loss, preeclampsia, Caesarean section, LGA, and neonatal hypoglycemia. We will use mixed models to analyze changes in repeated measures, such as glycemia variables and hypoglycemia fear scores by trimester. We will evaluate the percent of time spent in closed loop by trimester as a feasibility outcome that is important to the next step of a larger clinical trial with efficacy outcomes.

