
For women who discontinue CGM therapy during the study, we will do an intention to treat analysis of above-stated outcomes. The alpha level will be 0.05 for all analyses, except the non-inferiority tests (alpha = 0.025). The use of mixed models and Poisson regression will allow for analysis of data for the portion of the study completed with CGM therapy.

**Power and Sample Size Calculations:** The primary outcome for **Specific Aim 1** is percent of time spent <54 mg/dL on CGM. With a sample size of 10 women per group (20 study completers), we will have 80% power to detect non-inferiority using a one-sided alpha of 0.025 and a non-inferiority margin of 1.5% of time spent <54 mg/dL for HCL compared to SAPT, using estimates of variability from the PI's current study of CGM use during pregnancy. The standard deviation of time spent <54 mg/dL based on data from the PI's current study of CGM use during pregnancy was 1.1%. For **Specific Aim 2**, with a sample size of 10 women per group (20 study completers), we will have 83% power to detect a difference in time spent in target glucose range (65-140 mg/dL, this range was used in the power calculations because at that time there was no consensus on optimal time in range in pregnancy) of 3.3 hours/day (13.8%) between HCL to SAPT, assuming a standard deviation of 2.5 hours/day (effect size=1.0 SD). This is similar to effect sizes reported in another artificial pancreas study showing a difference of 2.5 hours/day (10.4%) between groups and a study of HCL in pregnancy (in a crossover design) showing a difference of 3.6 hours/day (15.2%). While this study is not powered to detect significant differences in maternal-fetal outcomes as described in **Specific Aim 4**, our goal is to provide estimates and preliminary data on these outcomes to inform the sample size needed for a larger trial focused on these outcomes, once the safety of the HCL system in pregnancy has been established.

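### The risk section says the sample size rests on comparing severe hypoglycemia rates, but the only power calculations are for CGM measures, and no main final analysis of severe hypoglycemia episodes is named

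*Combined protocol and SAP*

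**What the plan says.** **Sample-size basis.** Section IV.D (Risks) defines SH as an episode in which the woman needs a third party or hospitalization, and then states: "We have determined our sample size based on the ability to compare rates of severe hypoglycemia between groups".

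**Power section.** Under Power and Sample Size Calculations in Section IV.F, the Aim 1 primary outcome "is percent of time spent <54 mg/dL on CGM. With a sample size of 10 women per group", with 80% power for non-inferiority at a margin of 1.5%, SD 1.1% and one-sided alpha 0.025. The Aim 2 calculation is for a 3.3 hours/day difference in time in range with SD 2.5 hours/day. The section also carries a disclaimer for other outcomes: "While this study is not powered to detect significant differences in maternal-fetal outcomes". It has no corresponding sentence on SH.

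**Outcome status.** Section IV.A describes primary outcome 1 as safety "assessed through episodes of severe hypoglycemia and time spent with glucose <54 mg/dL". For Aim 1, Section IV.F says: "we will compare percent of time spent in the SH range of <54 mg/dL on CGM (primary outcome) using a non-inferiority t-test". SH episodes enter the final analysis only here: "As a secondary analysis of events such as SH, DKA, and skin reactions, we will account for potential differential follow-up times", by Poisson regression with a follow-up offset.

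**Interim look.** Sections IV.C and IV.F both plan, with the first 5 women per group, to "compare episodes of SH between groups to ensure no increased risk of SH with HCL therapy".

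**Shared label.** In several places the CGM threshold itself carries the SH label, for instance under Safety Factors in Section IV.C: "Time spent <54 mg/dL (SH range) will be collected through CGM data".

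**The concern.** Percent time below a CGM threshold and the rate of assisted hypoglycemic events are different quantities. The first is a continuous measure that every woman contributes. The second is a rare count. A sample size adequate for the first says nothing about the second.

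The sentence stands in the section that sets out participant risk. A reader there would conclude that the trial was built to compare SH rates, and so might take a final comparison with no difference as reassurance. Because Section IV.A puts SH episodes under a primary outcome while Section IV.F gives them no main final analysis, the plan also leaves open how that comparison will be made.

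**Working it through.** **1. Reproduce the plan's own figure.** Inputs from Section IV.F: n = 10 per group, margin 1.5, SD 1.1, one-sided alpha 0.025, true difference taken as zero.

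- Non-centrality = 1.5 / (1.1 × √(2/10)) = 3.049, with 18 df and critical t = 2.101.
- Power by non-central t = 82.2%. With n = 9 it is 77.5%, so 10 is the smallest n reaching 80%.
- Aim 2, normal approximation: Φ(3.3 / (2.5 × √(2/10)) − 1.96) = Φ(0.99) = 83.9%, against the stated 83%. By t-test it is 79.7%.

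Ten per group therefore comes from the CGM endpoints. (The analysis paragraph states a margin of 1%, not 1.5%; that is a separate matter.) No SH figure can be reproduced, because no SH rate, difference or margin is given.

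**2. Illustrate what 10 per arm can do for SH.** Assumptions:

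- SAPT rate from Section III, Preliminary Studies: 3 episodes, over an assumed 28 prospective or 36 analysed pregnancies. This is the only SH count in pregnancy in the documents.
- HCL triples the rate (my choice).
- Independent Poisson counts, equal follow-up, two-sided 0.05.

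Base rate: 3/28 = 0.107 or 3/36 = 0.083 per woman. The exact 95% interval for 3 events is 0.619 to 8.767, that is 0.022-0.313 per woman over 28, or 0.017-0.244 over 36.

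Power is the total probability of all pairs (x, y) of Poisson counts, with means 10r and 30r, that the test calls significant. The score statistic is (x − y)²/(x + y), and the exact test is the doubled-tail binomial. The Wald test uses ln(y/x)/√(1/x + 1/y), with a zero count treated as non-significant.

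| Base rate r | Score | Likelihood ratio | Exact | Wald |
|---|---|---|---|---|
| 0.107 | 15.6% | 26.0% | 4.3% | 0.7% |
| 0.083 | 11.2% | 21.9% | 2.0% | 0.2% |
| 0.313 (upper limit, 28) | 41.5% | 48.1% | 32.5% | 31.4% |
| 0.244 (upper limit, 36) | 32.5% | 41.2% | 23.2% | 17.9% |

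At the lower limits, power is under 3% for every test. The likelihood-ratio figures at the upper limits are flattered, since the true size of that test there is 8.7-9.5%.

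By the score or likelihood-ratio test, 80% power for a tripling needs about 68-88 women per arm (24-30 at the upper limits). With 10 per arm, 80% power is reached only at a rate ratio of about 8-11 (4.4-5.3 at the upper limits).

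**3. Sparse counts.** With equal rates, the chance that at least one arm has no SH is 1 − (1 − e^(−10r))² = 57% (3/28) or 68% (3/36). A Poisson rate ratio is then zero, infinite or undefined. At the upper limits the chance is 9-17%.

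**4. Interim look.** Even with a tripled rate and a whole pregnancy of exposure, the expected SH count in 5 HCL women is 5 × 0.321 = 1.6 or 5 × 0.25 = 1.25. The chance of none is e^(−1.607) = 20% or e^(−1.25) = 29%. The descriptions of this look also disagree:

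| Place | Timing | Measure |
|---|---|---|
| IV.C, Study Design | after 2nd trimester | SH episodes |
| IV.C, Data and Safety Monitoring Plan | after 1st trimester | SH events |
| IV.D, Safety Monitoring | after 1st trimester | especially glucose <63 |
| IV.F, interim safety analysis | after 1st trimester | SH episodes |

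Randomization is at the start of the 2nd trimester, so a look at the end of the 1st would contain essentially no HCL exposure.

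**The case against.** **Labelling slip.** The strongest reply is that the sentence uses SH loosely, since Sections IV.C and IV.F attach that label to glucose below 54 mg/dL, and Section IV.F is clear about the powered endpoint. That is plausible. But the same paragraph of Section IV.D defines SH as a clinical event, discusses its reporting as a serious event and speaks of rates. The correction is the same either way.

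**Primary against secondary.** A reader might infer that Section IV.F demotes SH to a secondary outcome, in flat contradiction of Section IV.A. The text does not go that far. A primary outcome can have a secondary analysis that adjusts for follow-up, and only DKA and skin reactions are tagged as secondary outcomes. What stands is the missing main final analysis.

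**Unprotected participants.** A reader might infer that SH goes unmonitored. It does not: the count-based stopping rules in Table 5, the notice of serious events to the DSMB within 1 business day, and the SMBG interim rule all stand apart from the sample-size claim. The interim SH review cannot be added to that list, because it is the look whose timing and measure conflict.

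**The illustration.** It rests on 3 events, an ambiguous denominator and a tripling of my choosing. One of the 2 affected women had two episodes, which fits poorly with independent counts. The pivotal study of this system in non-pregnant users had no SH. The trial's own rate could be lower (recent SH is an exclusion; risk is said to be highest in the 1st trimester) or higher (the background calls SH rates critically high; suspend features are disabled in SAPT mode). The plan names no test for the Poisson coefficient, so no single power figure belongs to it.

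**Conclusion.** The point holds and should be corrected. Section IV.D claims a design property that the trial does not have: 10 per group is derived from percent time below 54 mg/dL, and nothing in the documents derives it from SH events. This conclusion rests on the text alone.

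The size is illustrative. At the preliminary rate and an assumed tripling, power is about 2-26% (score, likelihood ratio, exact) or under 1% (Wald), and it does not exceed 48% at the upper limit of the base rate. These figures are conditional on the tripling; much larger ratios would be detectable. No direction of effect on SH is implied.

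Two further defects stand: no main final analysis is named for SH episodes, and 5 women per arm cannot ensure that there is no increased risk. It would go too far to say that the sample size is wrong for its CGM endpoint at the 1.5% margin, or that the plan commits to reading a null final SH comparison as proof of safety. No passage says that.

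**What to change.** 1. **Section IV.D, Risks.** Replace the sentence with: *The sample size is based on non-inferiority of HCL to SAPT in percent time <54 mg/dL on CGM (Section F). The trial is not powered to compare rates of severe hypoglycemia.* This matches the disclaimer already given for maternal-fetal outcomes.
2. **Sections IV.A and IV.F.** Give SH episodes one status and name their main analysis. One option is episodes and women affected per arm, with an exact 95% confidence interval for the rate ratio, which remains usable when one arm has no events. The follow-up-adjusted Poisson model can stay as the supplementary analysis.
3. **Sections IV.C and IV.F, interim look.** Replace the stated purpose with: *to review SH episodes by group*. Reconcile the timing and the measure across the four descriptions, and do not cite this look as a separate safeguard until that is done.

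Cost: wording in four sections and, if the option in item 2 is taken, one added interval. Sample size and stopping rules do not change. The downside is a more modest claim about SH safety.
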